9.3.2.1 Criteria for Evaluable Stool Fat Sample

The laboratory reported 24-hour stool fat value will be evaluable for analysis if the following condition is true.

• Stool collection in the corresponding 24-hour period is at least 67%. If stool collection data is missing or less than 67% of stool sample is collected, then the corresponding 24-hour stool fat value is not evaluable.

The stool fat (g) will be reported by lab for each subject per 24 hours period for 2 consecutive 24-hour collection periods (total 48-hour period) separately, prior to both Baseline (Day 1) visit and Week 1 (Day 8) visit. The average daily stool fat (g/day) at

both Baseline and Week 1 visit will be calculated from these two reported 24-hour stool fat for each subject. If the stool collection for a 24-hour period is evaluable with missing stool samples, then the total stool fat for that period will be adjusted following the imputation rule in Section 9.2.1. The average daily stool fat (g/day) at both Baseline and Week 1 visit will be calculated from the adjusted stool fat values for the analysis.

If the data on the "total bowel movements" and the "bowel movements not collected" is missing on any of the 4 days, then the stool fat will be regarded as missing for that day.

9.3.3 Supplementary Analyses of the Primary Efficacy Endpoint(s)

A supplementary analysis will be performed for the primary efficacy endpoint on the subjects included in the EAS-SF-SUPP (subjects with 100% stool sample collected for the 48 hour collection period at both Baseline (Day 1) and Week 1 visits) using the ATG-Day 1 group (High Dose and Low Dose) for the resected population. The change in stool fat from Baseline to Week 1 for each treatment group will be analyzed using the ANCOVA model described in Section 9.3.2.

9.4 Secondary and Additional Efficacy Analyses

9.4.1 Stool Fat

Resected Subjects

For comparison between dose cohorts for change in stool fat from Baseline to Week 1, the ANCOVA model including treatment as fixed effect and baseline stool fat as the covariate as described for the primary analysis will be used. The least square mean estimate of the difference between two treatment groups in change from baseline in stool fat will be provided along with the 95% CI and P value. The analysis will be performed using the EAS-SF and EAS-SF-SUPP set for the resected population only.

Non-Resected Subjects

The change in stool fat from Baseline to Week 1 will be analyzed using an analysis of covariance (ANCOVA) model including Baseline stool fat as the covariate. The least square mean estimates for change in stool fat along with its two-sided 95% CI will be provided. The null hypothesis of no change in mean stool fat from Baseline to Week 1 will be tested at 2- sided 5% α – level in EAS-SF.

9.4.2 Stool Frequency

Stool frequency is collected each day for 7 days prior to each visit during the study period. For the analysis, the average number of stool frequency per day is considered for the last 3 days prior to each visit (Day –3 to Day –1 for Baseline and Day 5 to Day 7 for Week 1 visit). The average stool frequency per day for a visit is defined as total number of stools in the last 3 days divided by 3 for that visit.

The analyses will be performed using the population and treatment groups as described in Table 1 in Section 4.2.

- For analysis of change in stool frequency from Baseline to Week 1, both within dose cohort and for comparison between dose cohorts (resected regimen only), an ANCOVA model including treatment as a fixed effect (resected population only) and Baseline stool frequency as the covariate will be used. Day -3, Day -2 and Day -1 would be considered for Baseline and Day 5, Day 6 and Day 7 would be considered for Week 1 visit.
- Descriptive summary statistics will be provided for change in stool frequency from Baseline to Week 1, 5, 9 and 13. For the summary, the average stool frequency per day for the Baseline and Week 1 is defined as total number of stool frequency in the last 3 days divided by 3 for that visit for comparison to Week 1. However, the average stool frequency per day for the Baseline and Week 5, 9 and 13 is defined as total number of stool frequency in the last 7 days divided by 7 for that visit for comparison to all other post-baseline visits.

• Descriptive statistics per day for stool frequency are presented specifying the mean, standard deviation, median, minimum and maximum of stool frequency for 7 days prior to Baseline and Week 1.

Sensitivity Analysis for Stool Frequency:

- For the sensitivity analysis, the average number of stool frequency per day is considered for the last 7 days prior to each visit. The average stool frequency per day for a visit is defined as total number of stool frequency in the last 7 days divided by 7 for that visit. Day -7 to Day -1 would be considered for Baseline and Day 1 to Day 7 would be considered for Week 1 visit.
- The 7-day mean will be analyzed similar to the primary analysis of the stool frequency using an ANCOVA model including treatment as a fixed effect (resected population only) and Baseline stool frequency as the covariate. Summary statistics and comparing the change in stool frequency from Baseline to Week 1 will also be summarized.

9.4.3 Stool Consistency

Stool consistency will be collected once a day for 7 days prior to each visit using the Bristol Stool Chart and will be characterized based on the typology below for the analysis. The proportion of days with watery consistency during 7-day period prior to each visit will be calculated at each visit for each subject. The analyses will be performed using the population and treatment groups as described in Table 1 in Section 4.2.

- A Wilcoxon paired signed rank test will be performed for comparison of the proportion of days with watery stool consistency of Week 1 to that at Baseline within each dose cohort in the resected population. Similar test will be performed in the non-resected population as well.
- For comparison of change in the proportion of days with watery stool consistency from Baseline to Week 1 between two dose cohorts will be assessed through the non-parametric Wilcoxon Rank-Sum test in the resected population.

- Descriptive statistics will be provided for proportion of days with watery stool consistency at Week 1 (Day 8), 5, 9 and 13 as well as change from Baseline for each visit in both the resected and non-resected population.
- The number and percentages of subjects with 7 different types of stool consistency reported and 2 different types of characterization of stool consistency as described in Table 3 will be summarized per day for 7 days prior to Baseline (Day 1) and 7 days prior to Week 1 (Day 8) visit for the non-resected population and for each analysis treatment group in the resected population.

Table 3. Characterization of Bristol Stool Chart for Analysis

Stool Type (Score)	Characterization
Type 1 (1), Type 2 (2), Type 3 (3), Type 4 (4), Type 5 (5)	Hard/Normal
Type 6 (6), Type 7 (7)	Watery

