3.2 Secondary Endpoint(s)

Resected Pancreatic Cancer Subjects

- Change from Baseline to Week 1 in average daily stool frequency. The average daily stool frequency is calculated from the last 3 days prior to each of Baseline and Week 1 visit.
- Change from Baseline to Week 1 in stool consistency, based on the proportion of days having watery stool consistency in the last 7 days prior to each of Baseline and Week 1 visit.
- Change from Baseline to Week 1 in the total EPI Symptoms Score.

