9.0 Efficacy Analyses

9.1 General Considerations

The primary efficacy analyses will be conducted in the EAS-SF and EAS-SF-SUPP for the supplementary analysis of the stool fat. All other efficacy analyses will be conducted

in the FAS population, considering different groups for different analysis as tabulated in Table 2 in Section 4.2. All tests will be 2-sided at an alpha level of 0.05.

The Primary Analysis and other analyses will be performed after all subjects in the resected and non-resected population have completed the study and the database has been locked. This will be the only and final analysis for the primary and secondary efficacy endpoints as well as all other efficacy endpoints in the study.

"Baseline" refers to the last non-missing observation before the first administration of study drug or randomization if no study drug is given, unless otherwise specified in the individual analysis section.

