9.4.4 EPI Symptom Score

EPI symptom score for the efficacy analysis will be calculated at each visit as the total score for the responses to all the 12 questions in the EPI Symptoms Questionnaire. The response score will range from 0 to 4 for each question (0 corresponding to None to 4 corresponding to Very Severe). Therefore, the total score will range from 0 to 48.

The analyses will be performed using the population and treatment groups as described in Table 1 in Section 4.2.

- Change in EPI Symptom Score from baseline to Week 1 will be analyzed similarly to the stool frequency analyses using an ANCOVA model including treatment as a fixed effect (resected population only) and Baseline EPI Symptom score as the covariate for both within dose cohort and for comparison between dose cohorts (resected population only).
- Similar analyses will also be provided for the subset of questions (Question 7, 8 and 10) used for dose modification criteria (resected population only).

- Descriptive summary statistics will be provided for change in EPI Symptom score from Baseline to Week 1, 5, 9 and 13 in both the resected and non-resected population.
- Descriptive statistics per day for EPI Symptom score are presented specifying the mean, standard deviation, median, minimum and maximum of stool frequency for 7 days prior to Baseline (Day 1) and Week 1 (Day 8).

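### The Week 1 between-dose test of stool consistency omits the baseline covariate used in the other tested Week 1 between-dose comparisons; it is valid but gives up some power

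*SAP*

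**What the plan says.** SAP 3.2 lists the endpoint as secondary: "Change from Baseline to Week 1 in stool consistency, based on the proportion of days having watery stool consistency". SAP 9.4.3 defines the measure: "The proportion of days with watery consistency during 7-day period prior to each visit will be calculated at each visit for each subject". Bristol types 6 and 7 count as watery. SAP 9.2.4 allows the proportion to rest on 4 to 7 observed days.

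For the difference between doses in change to Week 1, SAP 9.4.3 says that it "will be assessed through the non-parametric Wilcoxon Rank-Sum test in the resected population". It names no covariate, no rank ANCOVA and no effect estimate with an interval for this comparison.

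The other Week 1 between-dose tests are specified differently:
- Stool fat (SAP 9.4.1): "the ANCOVA model including treatment as fixed effect and baseline stool fat as the covariate".
- Stool frequency (SAP 9.4.2): "an ANCOVA model including treatment as a fixed effect (resected population only) and Baseline stool frequency as the covariate will be used".
- EPI symptom score (SAP 9.4.4): an ANCOVA with "Baseline EPI Symptom score as the covariate for both within dose cohort and for comparison between dose cohorts".

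Quality of life is only summarised descriptively in the SAP. SAP 9.1 sets the level: "All tests will be 2-sided at an alpha level of 0.05". SAP 12.0 plans no multiplicity adjustment. The SAP does not say why stool consistency is handled differently.

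**The concern.** The proportion lies between 0 and 1. A subject with 0/7 watery days at Baseline cannot improve, and one with 7/7 cannot worsen, so the possible change depends on where the subject starts. The eligibility criteria do not require watery stools, so subjects at the floor can be enrolled. Ranking the change does not remove this dependence.

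The raw change also carries all the day-to-day noise of a short baseline diary. Baseline data are already collected from Day -7 to Day -1, so a covariate needs nothing new. At stake is the power and precision of one of the three Week 1 endpoints in SAP 3.2, and how far its result depends on chance differences at Baseline in an unstratified trial with 72 resected subjects.

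**Working it through.** **1. The plan's own power figure.** SAP 2.4 gives between-dose power for stool fat only: 60 evaluable (30 per arm), SD 25 g, two-sided 0.05. The standard error is 25 × √(2/30) = 6.45 g. Noncentrality is 20/6.45 = 3.10 or 15/6.45 = 2.32. The noncentral t with 58 df gives 86.1% and 62.8%, against the stated 86% and 63%. The plan has no such figure for stool consistency, so every size below rests on assumed inputs.

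**2. Normal theory.** Let both visits have variance σ² and correlation r.
- Variance of change: 2σ²(1 − r).
- Residual variance in ANCOVA: σ²(1 − r²).
- Ratio: (1 + r)/2.

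The efficient baseline slope here is r, whereas change fixes it at 1. Example at r = 0.5: the ratio is 0.75, noncentrality rises from 2.32 to 2.32/√0.75 = 2.68, and power rises by about 12 points.

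Gain from a starting power of 63%, 30 per arm:

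| r | 0 | 0.2 | 0.3 | 0.4 | 0.5 | 0.6 | 0.7 | 0.8 | 0.9 |
|---|---|---|---|---|---|---|---|---|---|
| Gain (points) | 27 | 21 | 18 | 15 | 12 | 10 | 7 | 4.5 | 2 |

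A gain of 10 to 20 points corresponds to r of roughly 0.25 to 0.6.

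**3. Simulation on the bounded scale.** Assumptions: 7 binary days per visit, Baseline centred at 50% watery, normal subject effects on the logit scale, visit noise SD 0.8, logit dose effect 1.0, 36 per arm, 2,000 replicates. The Monte Carlo standard error is about √(0.6 × 0.4/2000) = 1.1 points.

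| Subject SD | Correlation | Rank-sum on change | Rank ANCOVA | Gain |
|---|---|---|---|---|
| 0.8 | 0.31 | 66% | 87% | 21 |
| 1.2 | 0.49 | 63% | 77% | 14 |
| 1.8 | 0.66 | 59% | 71% | 12 |

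At 30 per arm the same three settings give 56% to 77%, 56% to 72% and 49% to 59%, which are gains of 21, 16 and 10.

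Less favourable assumptions, 36 per arm, rank ANCOVA:
- Subject SD 2.5 or 3.5 (correlation 0.75 or 0.83): +8 and +6. A separate run at correlation 0.85 gave about +4.
- Visit noise 0.3 with subject SD 3.5 (correlation 0.88): +3.
- 40% of subjects almost never watery: +8 (SD 0.8) and +2 (SD 1.8); a separate run gave about +5. In the least favourable of these, ordinary ANCOVA still rose from 33% to 44%.

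A wider grid of 60 scenarios used baseline mean 0.3 to 0.7, subject SD 1.5 or 2.5, latent correlation 0.3 to 0.95 and 0 to 50% never watery. Ordinary ANCOVA gained 4 to 44 points over the rank-sum, with 43% of scenarios between 10 and 20. Rank ANCOVA was generally close to it, and lower in some scenarios with many never-watery subjects.

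**4. Type I error.** It was 4.5% to 5.2% in one set of runs and about 4% to 6% in the others, for adjusted and unadjusted tests alike.

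**5. Dependence on chance imbalance.** In the middle setting (SD 1.2, 36 per arm), take the trials whose baseline difference exceeds one standard error, roughly one in three. Rank-sum power was 33% or 91%, depending on which arm started worse; rank ANCOVA stayed at 78% to 79%. With no true effect, false positives in such trials were 6% to 10% for the rank-sum across settings, against 3% to 5% for rank ANCOVA.

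**The case against.** The SAP's choice is coherent. A rank test suits a tied, bounded proportion built on 4 to 7 days. It pairs with the within-cohort signed-rank test in the same section, and it tests the endpoint as written, which is a change from Baseline. Using a different method for a differently distributed endpoint is not in itself an inconsistency. The comparison is unpowered, secondary and without multiplicity control, in a study that SAP 12.0 describes as not for registration. All of this stands, and it limits the point to efficiency.

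A reader might go further in four ways that the documents do not support:
- **That the plan loses a known 10 to 20 points of power.** No input for this endpoint is given, and that range is only part of what plausible assumptions produce.
- **That the test gives no protection against baseline imbalance.** Change subtracts the baseline value. The fault is the fixed slope of 1, which over-corrects.
- **That the rank-sum is wrong.** Randomisation makes it valid, and its overall type I error held in simulation.
- **That rank ANCOVA is the only remedy.** With many never-watery subjects it gained least in some settings, while ordinary ANCOVA did as well or better and gives a difference in interpretable units.

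**Conclusion.** The point holds as an efficiency improvement. SAP 9.4.3 leaves out an available covariate that the other tested Week 1 between-dose comparisons use, and gives no reason. Adjustment gained power in every scenario run.

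The size depends on the baseline/Week 1 correlation and on how many subjects sit at the floor, neither of which the documents give. The ranges for 36 per arm also assume a logit dose effect of 1.0, and most of them a Baseline centred at 50% watery. The direction is secure; the size is not. Nothing here makes the planned test invalid.

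**What to change.** Before unblinding, amend the between-dose bullet in SAP 9.4.3 to a baseline-adjusted analysis. The simplest choice is the ANCOVA already used for stool frequency and EPI score: change in the proportion of watery days as response, dose as fixed effect, baseline proportion as covariate, reporting the adjusted difference with its 95% CI. The endpoint in SAP 3.2 is unchanged, because with baseline in the model the dose coefficient is the same whether the response is the change or the Week 1 value. If a rank method is preferred, use a rank ANCOVA: Week 1 rank on dose and baseline rank. Keep the rank-sum on change as a sensitivity analysis. If the sponsor retains the rank-sum as the main test, the SAP should say why this endpoint is treated differently.

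The cost is a few lines of SAP text and code, with no new data. There are two drawbacks. ANCOVA on a bounded, tied proportion relies on a large-sample approximation. Rank ANCOVA gives an estimate on the rank scale, so medians by cohort should be shown beside it.

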9.4.4 EPI Symptom Score

EPI symptom score for the efficacy analysis will be calculated at each visit as the total score for the responses to all the 12 questions in the EPI Symptoms Questionnaire. The response score will range from 0 to 4 for each question (0 corresponding to None to 4 corresponding to Very Severe). Therefore, the total score will range from 0 to 48.

The analyses will be performed using the population and treatment groups as described in Table 1 in Section 4.2.

- Change in EPI Symptom Score from baseline to Week 1 will be analyzed similarly to the stool frequency analyses using an ANCOVA model including treatment as a fixed effect (resected population only) and Baseline EPI Symptom score as the covariate for both within dose cohort and for comparison between dose cohorts (resected population only).
- Similar analyses will also be provided for the subset of questions (Question 7, 8 and 10) used for dose modification criteria (resected population only).

- Descriptive summary statistics will be provided for change in EPI Symptom score from Baseline to Week 1, 5, 9 and 13 in both the resected and non-resected population.
- Descriptive statistics per day for EPI Symptom score are presented specifying the mean, standard deviation, median, minimum and maximum of stool frequency for 7 days prior to Baseline (Day 1) and Week 1 (Day 8).

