#### Resected Pancreatic Cancer Subjects

- Difference between 2 dose cohorts in change from Baseline in stool fat at Week 1
- Stool frequency at Weeks 1, 5, 9, and 13 comparing to Baseline, and the difference in change from Baseline to Week 1 between 2 dose cohorts
- Stool consistency at Weeks 1, 5, 9, and 13 comparing to Baseline, and the difference in change from Baseline to Week 1 between 2 dose cohorts
- EPI symptoms at Weeks 1, 5, 9, and 13 comparing to Baseline, and the difference in change from Baseline to Week 1 between 2 dose cohorts
- Quality of life (QoL) (European Organisation for Research and Treatment of Cancer [EORTC] Quality of Life Questionnaire [QLQ]-C30 and QLQ PAN26) at Weeks 1, 5, 9, and 13 comparing to Baseline, and the difference in change from Baseline to Week 1 between 2 dose cohorts
- Body weight and body mass index (BMI) at Weeks 1, 5, 9, and 13 comparing to Baseline
- Chemotherapy tolerability
- Serum albumin and pre-albumin at Weeks 5, 9 and 13 comparing to Baseline

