## Disease Activity

- ✓ 9. Subject has been diagnosed with pancreatic cancer with biopsy and/or radiography, with a life expectancy of at least 5 months at Screening Visit.
- ✓ 10. Subject's pancreatic cancer must involve the head and/or neck of the pancreas.
- ✓ 11. Subject must have an Eastern Cooperative Oncology Group (ECOG) performance status of 0 to 2 or Karnofsky performance status (PS) > 60%.
- ✓ 12. Subject must have stable organ and marrow function as defined below:
  - Absolute neutrophil count (ANC) > 500/ $\mu$ L;
  - Platelets > 50,000/ $\mu$ L;
  - Total bilirubin  $\leq$  4  $\times$  upper limit of normal (ULN);

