3.3 Additional Endpoint(s)

Resected Pancreatic Cancer Subjects

- Average daily stool frequency for 7 days prior to each of Weeks 5, 9 and 13 visits compared to Baseline visit.
- Stool consistency in the 7 days prior to each of Weeks 5, 9 and 13 visits compared to Baseline visit.
- Total EPI Symptom Score at Weeks 5, 9 and 13 visits compared to Baseline visit.
- The scaled total score for each scale/item as described below of Quality of life (QoL) (European Organisation for Research and Treatment of Cancer [EORTC] Quality of Life Questionnaire [QLQ]-C30 and QLQ PAN26) at Weeks 1, 5, 9, and 13 visits compared to Baseline visit.

QLQ-C30:

- Global health status/QoL.
- Functional scales (Physical functioning, Role functioning, Emotional functioning, Cognitive functioning, Social functioning).
- Symptom scales/items (Fatigue, Nausea and vomiting, Pain, Dyspnoea, Insomnia, Appetite loss, Constipation, Diarrhoea, Financial difficulties).

QLQ-PAN26:

- Pancreatic Pain.
- Digestive symptoms (Gastrointestinal).
- Hepatic (Jaundice).
- Altered bowel habit.
- Poor body image.
- Satisfaction with health care.
- Sexuality (Sexual dissatisfaction).
- Body weight and body mass index (BMI) at Weeks 1, 5, 9 and 13 visits compared to Baseline visit.
- Chemotherapy tolerability (as defined in Section 9.4.6).
 - Difference in expected or planned chemotherapy from the last scheduled visit (Yes / No / Not Applicable, no chemotherapy planned) at Week 1, 5, 9 and 13 visits.
 - Proportion of expected or planned chemotherapy due to chemotherapy tolerability.
 - Proportion of different types of changes due to chemotherapy tolerability (entire regimen permanently discontinued / one or multiple agents permanently discontinued / dose held / dose interrupted / dose reduced / change in treatment administration schedule).
 - Diagnosis of changes due to chemotherapy tolerability (Adverse events / Medical history).
- Serum albumin and pre-albumin level at Weeks 1, 5, 9 and 13 compared to Baseline.

Non-Resected Pancreatic Cancer Subjects

- Change in stool fat from Baseline (Day 1) to Week 1 (Day 8).
- Change from Baseline to Week 1, 5, 9 and 13 in average daily stool frequency. The average daily stool frequency is calculated from the last 7 days prior to each of Baseline and Weeks 1, 5, 9, and 13 visits.

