9.2.2 Missing EPI Symptoms Score

The EPI Symptoms Questionnaire data will be used to compute the EPI Symptom score. Each of the 12 questions is scored as described in Dose modification, Section 2.5. The missing answers to any of the 12 questions of the EPI questionnaire will not be possible unless the subject did not complete the EPI questionnaire at all. The questionnaire can be submitted only when all the questions in the questionnaire have been answered. No questions can be skipped before submitting. Missing EPI questionnaire will not be imputed.

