9.4.7 BMI, Body Weight

The change from baseline to each visit in body weight, BMI, hip and waist circumference, will be summarized from Baseline (Day 1) to each post baseline visit using descriptive statistics.

The number and percentage of subjects who had more than $10\% (\ge 10\%)$ reduction in their body weight and for subjects who had more than $10\% (\ge 10\%)$ increment in their body weight for each visit will also be summarized.

Body Mass Index (BMI) is calculated as follows at each visit:

BMI $(kg/m^2) =$ Body Weight (kg) / Body Height2 (m^2) :

The analyses will be performed in both the resected and non-resected population using the population and treatment groups as described in Table 1 in Section 4.2.

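### The protocol's secondary endpoints at Weeks 5, 9 and 13 get only descriptive observed-visit summaries, with no interval, longitudinal model or missing-data sensitivity analysis; if subjects with poor change leave, later improvement is overstated.

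*SAP*

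**What the plan says.** **Endpoint status.** Protocol 3.3 lists, as secondary for resected subjects, "EPI symptoms at Weeks 1, 5, 9, and 13 comparing to Baseline", with matching entries for stool frequency, stool consistency, quality of life and weight/BMI. Albumin and pre-albumin are secondary at Weeks 5, 9 and 13. The protocol prescribes no method for these visits and leaves detail to the SAP.

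SAP 3.2 keeps only Week 1 results as secondary, for example "Change from Baseline to Week 1 in the total EPI Symptoms Score". SAP 3.3 lists the later visits as additional: "Total EPI Symptom Score at Weeks 5, 9 and 13 visits compared to Baseline visit". SAP 1.0 sends the reader to Section 12.0 for changes from the protocol, but that section deals only with type I error.

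**Analysis.** For stool frequency (SAP 9.4.2): "Descriptive summary statistics will be provided for change in stool frequency from Baseline to Week 1, 5, 9 and 13". For EPI symptoms (9.4.4): "Descriptive summary statistics will be provided for change in EPI Symptom score from Baseline to Week 1, 5, 9 and 13". Weight and BMI (9.4.7) "will be summarized from Baseline (Day 1) to each post baseline visit using descriptive statistics". Stool consistency (9.4.3), quality of life (9.4.5) and albumin/pre-albumin (9.4.8) are also descriptive; albumin and pre-albumin add a final post-baseline summary. Where SAP 7.0 spells out descriptive statistics for continuous data, it names n, mean, SD, median, minimum and maximum, and no interval.

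**Missing data.** SAP 9.2.2: "Missing EPI questionnaire will not be imputed". The rules for stool diaries and quality-of-life items work within a visit. SAP 8.0 covers only Week 1 stool fat.

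**Grouping.** SAP 4.1 and Table 1 group by-visit stool and patient-reported results by the dose dispensed at the prior visit (ATG-Dynamic). SAP 2.5 triggers escalation from three EPI items.

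**The concern.** A Week 13 summary of observed visits describes the people still being measured. If those who left had fared worse since Baseline, it flatters the treatment, and nothing planned would show by how much. Separately, the grouping rule selects on symptoms: low-dose subjects whose symptoms stay high move into the high-dose column. A difference between the dose columns after Week 1 may then reflect who was moved rather than dose. At stake is how far the 13-week symptom, weight and nutrition results can be relied on; the protocol ranks them as secondary.

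**Working it through.** **1. The plan's own figures.** The only quantitative planning is for Week 1 stool fat. 72 × (1 − 0.16) = 60.5 evaluable, or 30 per cohort. Noncentral-t power is then 98.9% and 94.2% within cohort and 86.1% and 62.8% between cohorts, against 99%, 94%, 86% and 63% stated. These reproduce. No retention, SD or precision is given for Weeks 5, 9 or 13, so everything below is in SD units over assumed ranges.

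**2. Size of the bias, by identity.** With a fraction d missing,

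observed mean change − true mean change = d × (mean change in stayers − mean change in leavers).

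For stayers better by 0.25, 0.5 or 1 SD:
- d = 16%: 0.04, 0.08, 0.16 SD
- d = 30%: 0.075, 0.15, 0.30 SD
- d = 40%: 0.10, 0.20, 0.40 SD

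**3. Simulation, dropout driven by change.** Assumed: Baseline plus four visits, equal variances, correlation 0.7, no true change, dropout after Week 1, and odds of leaving multiplied by 1.6 to 2.7 per SD of worse change at the last visit. Bias toward benefit in mean change at Week 13, in SDs of the change score:

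| Retention | Compound symmetry | AR(1) |
|---|---|---|
| 75% | 0.06-0.12 | 0.07-0.14 |
| 65% | 0.09-0.17 | 0.11-0.21 |
| 55% | 0.12-0.22 | 0.15-0.27 |

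For scale, with 36 per arm, 75% retention leaves 27 subjects (SE 1/√27 = 0.19 SD) and 55% leaves about 20 (SE 1/√20 = 0.22 SD). The bias therefore runs from about a third of a standard error (0.06/0.19) to slightly above one (0.27/0.22).

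**4. Same question with a true improvement.** Assumed: 72 subjects, true change −0.50 (in SDs of a single visit), correlation 0.6 compound symmetry or 0.8 AR(1), and 16%, 30% or 40% dropout. The observed-visit mean was −0.56, −0.62, −0.66 (compound symmetry) or −0.60, −0.68, −0.75 (AR(1)). Its nominal 95% interval covered the truth 92%, 85%, 79% or 89%, 77%, 66% of the time. A likelihood estimate using all earlier visits returned about −0.50 throughout.

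**5. Other dropout mechanisms.** When leaving depends on symptom level rather than change, bias in mean change is under 0.01 SD: stayers also had better Baselines, and the two effects cancel. The cancellation relies on the equal variances and symmetric correlations assumed here. When better subjects leave (30% dropout, settings of step 4, compound symmetry), the observed mean is −0.38 against −0.50, so improvement is understated.

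**6. Grouping alone, with no dropout.** Apply the SAP 2.5 rule at Week 1 (three-item score above 2 and above 0.7 × the previous score) with no dose effect. Assumed scores: Baseline mean 5, mean 4 afterwards, SD 2.5, correlation 0.6, range 0 to 12. About 55% of the low arm escalates. Mean later change is −0.97 in both randomised arms but −1.48 in the dynamic low group and −0.82 in the dynamic high group. Check: the low group holds 0.5 × (1 − 0.546) = 0.227 of subjects, and 0.227 × (−1.48) + 0.773 × (−0.82) = −0.97. Two other sets of means gave −2.46 against −1.75 and −2.22 against −1.72. The overall column is unaffected.

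**The case against.** The documents do not show that later results will look better than they are, though a reader might infer it. They give no retention after Week 1 and no link between leaving and outcome, and the 16% concerns evaluable Week 1 stool fat only. The entry criterion, "with a life expectancy of at least 5 months at Screening Visit", cannot carry the inference either: up to 56 days of screening plus 91 of treatment is 147 days, just under five months (5 × 30.4 = 152), so it selects people expected to reach Week 13. All of this stands, and the direction is stated here only as a condition.

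The plan also limits the loss. Protocol 5.5 keeps subjects who stop study drug in scheduled visits, the discontinuation visit collects the same measures, and the final post-baseline albumin summary retains anyone with a later value. This reduces the problem but does not cover withdrawal of consent or death. The SAP does not say whether discontinuation-visit data count as Week 13 for these endpoints.

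Two further readings fail. SAP 9.2 does not contradict itself by promising imputation: it announces the methods that follow, and one of them is not to impute the EPI questionnaire. The absent interval does not cause bias, and adding one to observed-visit means would not cure it (step 4); from n, mean and SD a reader could compute it.

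Finally, the study is declared non-registrational, and chemotherapy may start after Week 1, so within-arm change does not isolate a drug effect. Descriptive reporting is therefore defensible as a minimum. That limits the weight of the point, but does not explain why endpoints ranked secondary in the protocol have no missing-data plan.

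**Conclusion.** The point holds as a gap in the analysis, not as a demonstrated bias. The move from secondary to additional is unexplained, and the later visits have no interval, longitudinal model or missing-data sensitivity analysis. Overstatement of about 0.06-0.27 SD of the change score requires dropout tied to poor change from Baseline and retention of 55-75%, both assumed. Under dropout by symptom level it is close to nil, and if better subjects leave the sign reverses. Separation of the dose groups through ATG-Dynamic needs no dropout; its size rests on assumed scores, and it concerns stool and patient-reported results only. The primary endpoint and Week 1 comparisons are untouched. This is a worthwhile, inexpensive improvement.

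**What to change.** Keep the descriptive tables. For the continuous endpoints in resected subjects of the full analysis set, add a mixed model for repeated measures by randomised arm, with Baseline value, visit, arm and arm by visit, and unstructured covariance. Report least-squares mean change with a 95% interval at each scheduled visit (Weeks 5, 9 and 13 only for albumin and pre-albumin). For stool frequency use the 7-day mean throughout, since SAP 9.4.2 otherwise mixes 3-day and 7-day windows. The proportion of watery days is bounded and is rank-tested at Week 1, so it can stay in the tables.

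Also:
- state how discontinuation-visit data map to scheduled visits;
- report numbers and reasons missing at each visit, by randomised arm;
- add a delta-adjusted sensitivity analysis that worsens missing values in steps, for example 0.25, 0.5 and 1 SD;
- explain the change of endpoint status and correct the pointer to Section 12.0.

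The cost is SAP wording and one standard model per endpoint, on data already collected. The model assumes data missing at random, which is weaker than what observed-visit means need but cannot be verified; hence the delta analysis. The randomised-arm result includes the effect of dose escalation and must be labelled as such. ATG-Dynamic tables should carry a note that group membership depends on earlier symptoms.
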